## 2. SYNOPSIS

Name of Sponsor/Company: Exonate Ltd.	
Name of Investigational Product: EXN407	
Name of Active Ingredient: [REDACTED]	
Protocol Number: PQ-110-001	
Title of Study: A Randomized, Double-Masked Vehicle-Controlled, Multiple Dose, Dose Escalation Study to Evaluate the Safety and Tolerability of EXN407 in subjects with Center Involved Diabetic Macular Edema secondary to Diabetes Mellitus.	
Study Center(s): The trial will be conducted at up to 17 study centers globally.	
Studied Period (Years): Estimated date first subject enrolled: Oct 2020 Estimated date last subject completed: Aug 2022	Phase of Development: Phase Ib/II
Objectives: Primary: 

To evaluate the ocular safety and tolerability of EXN407 ophthalmic solution in subjects with diabetic macular edema (DME) secondary to diabetes mellitus

 Secondary: 

Safety: To evaluate the systemic safety and tolerability of EXN407 ophthalmic solution in subjects with DME secondary to diabetes mellitus

Safety: To evaluate changes in ocular functional and structural measures with the use of EXN407 ophthalmic solution in subjects with DME secondary to diabetes mellitus

Pharmacokinetics (PK): To evaluate the systemic pharmacokinetics of EXN407 ophthalmic solution in subjects with DME secondary to diabetes mellitus

	

**Outcome Measures:****Safety****Primary:**

- Frequency and severity of ocular adverse events (AEs) in the treatment and contralateral eyes

**Secondary:**

[figure not shown]
- Frequency and severity of non-ocular AEs
- Changes from baseline in safety parameters, including vital sign measurements, physical examination findings, electrocardiogram (ECG), and laboratory parameters
- Changes from baseline in ophthalmic examination findings, including ophthalmoscopy

[figure not shown]
***Safety***

- Change from baseline in Center-Subfield Macula Edema (center-subfield measure)
- Change from baseline in macular fluid volume
- Change from baseline in best corrected visual acuity (BCVA) using the early treatment diabetic retinopathy study (ETDRS) visual acuity scale
- Change from baseline in fluorescein fundus angiography (FFA)
- Change from baseline in corneal thickness based on pachymetry assessed at a consistent time of day
- Change from baseline in corneal endothelial cell count (dose expansion cohort)

***Pharmacokinetics***

- Characterize the PK profile of EXN407 in plasma (dose escalation and dose expansion cohort[s])

**Methodology:****General**

This is a first in human (FIH), Phase Ib/II study of EXN407. It is a randomized, double-masked, vehicle-controlled, multiple dose, dose-escalating study to evaluate the safety and tolerability of EXN407 in subjects with center involved DME, with CMT between 280-420  $\mu\text{m}$  and BCVA better than or equal to a 69 ETDRS score (an approximate Snellen equivalent of 20/40 or 6/12). For brevity these criteria may also be written as “better than or equal to a 69 ETDRS score” in the study eye, which is considered secondary to diabetes mellitus.

The Screening period is from 28 to 3 days prior to randomization and the start of study treatment (i.e., from study days -28 to -3). Subjects that meet all eligibility criteria as assessed by the evaluating Investigator at Screening will enter a run-in period (from post-screening to Day -1) where the subject (or subject’s partner as applicable) will administer Systane Ultra UD eye drops twice per day (BID) using Systane Ultra unit-dose (UD) droppers. The run-in period serves to familiarize and train subjects in topical administration via eye dropper. Please refer to Section 12.2 for more details on the run-in period.

***Selection of Study Eye***

EXN407 or vehicle-control solution will be administered unilaterally to the study eye only. The Investigator should identify the eye in which evident center involved DME is present with a CMT between 280-420  $\mu\text{m}$  as determined by SD-OCT and all other inclusion/exclusion criteria are met. All SD-OCT assessments for a subject should be taken with the same make and model of equipment throughout the duration of the study.

If both eyes qualify on the basis of evident DME with CMT of between 280-420  $\mu\text{m}$ , and other inclusion/exclusion criteria, then the Investigator should choose the eye with the worse (greater) CMT as the study eye. If CMT is the same, then the eye with worse visual function as assessed by BCVA will be selected as the study eye. If both eyes have the same BCVA then the right eye will be selected.

***Dose Escalation (A) Cohorts***

The study will assess the safety and tolerability of EXN407 at up to three escalating dose (concentration) levels and placebo (vehicle) consisting of an excipient formulation adjusted for osmolality. EXN407 or vehicle-control will be administered as a single 30  $\mu$ L drop unilaterally to the study eye only, and the drops will be administered BID for 7 days. Subjects will be assessed for safety, tolerability and efficacy at follow-up visits.

***Analysis and Adaptive Design***

All visit-based data will be analyzed for the study eye at each visit as well as change from baseline. Comparisons with the non-dosed contralateral eye will also be evaluated in each subject. All protocol evaluations will also be completed on the non-dosed contralateral eye. No vehicle-control or other study treatments will be administered to the contralateral eye. The response to active treatment will be compared to vehicle on a group basis (pooling vehicle subjects).

The protocol is adaptive regarding the number and size of cohorts and dose level progression, which will be informed by emergent data and documented decision making by the dose escalation committee (DEC) following review of available safety and tolerability data from each cohort. The dose levels proposed in this protocol can potentially be reduced or altered based on DEC review.

***Allocation to Study Treatment***

Sequential dose cohorts of EXN407 (with vehicle-control) are planned.

With exception of the first cohort, each of the remaining ascending dose cohorts will consist of 4 subjects (3 subjects randomized to receive EXN407 and 1 subject randomized to receive vehicle). Of note, the first cohort will incorporate an additional subject to provide a sentinel dosing subgroup (2 subjects, 1 subject randomized to receive EXN407 and 1 subject randomized to receive vehicle) followed after an interval of at least one week by the remaining subjects (2 subjects randomized to receive EXN407 and 1 subject randomized to receive vehicle).

The interval between cohorts, and between the sentinel pair and the remainder of the first cohort, will be at least 1 week.

Each eligible subject in the dose escalation cohorts (numbered cohorts 1, 2, 3, etc.) will receive EXN407 or vehicle BID in 14 doses (1 drop of 30  $\mu$ L at each dosing occasion, therefore 14 drops in total; with the contingency that if the first drop is not properly administered a second drop can be administered at the time) over a 7 day period.

***Dose Expansion (E) Cohort***

The highest well-tolerated dose of EXN407 (as recommended by the DEC) will be evaluated in a subject expansion cohort consisting of up to a maximum of 40 subjects (randomized to receive EXN407 at the selected dose or vehicle, in a 2:1 ratio). Each eligible subject in the expansion cohort will receive study drug for up to 84 days, resulting in a total of 168 doses (168 single drops 30  $\mu$ L volume) of EXN407 or vehicle.

***Stopping Criteria and Dose Holding***

Subjects who do not meet individual subject stopping criteria at the clinical evaluation visits will continue dosing until final day of dosing. Subjects who meet the stopping criteria will be discontinued from dosing but continue to receive safety and efficacy evaluation and all

scheduled clinical assessments as well as follow-up at an EOS Visit 28 days post the subject's last dose where possible.

Detailed stopping criteria for individual subjects and guidance for study Investigators are provided in Section 8.5.1.1. However, these criteria include an increase from baseline in CMT of  $>75 \mu\text{m}$  and a loss of 15-letters of vision. In the case of these two specific stopping criteria being met, at the discretion of the Investigator, rescue medication comprising a marketed anti-VEGF therapeutic will be made available to the patient. The Sponsor would reimburse the cost to the site to a maximum of two doses, or until the drug became approved by the Pharmaceutical Benefit Scheme or other health insurance, whichever occurs first.

The study Investigator in conjunction with the study MM [REDACTED] and also Sponsor's MM may decide to discontinue study drug for an individual subject, based on pre-defined decision rules for reasons of safety. Subjects who discontinue study drug will continue to be followed for safety and efficacy outcomes for the remainder of the study.

Detailed stopping criteria for cohorts are provided in Section 8.5.2. Current cohort doses can be held, and dose escalations planned for the next cohort can be stopped based on cohort stopping criteria, until discussion by the Principal Investigator (PI), DEC, study MM [REDACTED] and also the Sponsor MM has resulted in a decision.

#### *Proposed Doses*

The proposed doses are:

- Placebo (vehicle, i.e., excipient only)
- Low-Dose 0.5 mg/mL (0.05%) EXN407, one drop administered twice per day
- Mid-Dose 1 mg/mL (0.1%) EXN407, one drop administered twice per day
- High-Dose 1.5 mg/mL (0.15%) EXN407, one drop administered twice per day

#### *Initial Dosing and Dose Escalation*

No intra-subject dose escalation/de-escalation will occur.

Safety review will be conducted by the DEC before each cohort initiating dosing, and on an ad hoc basis as needed. The Sponsor will also perform safety review on an ongoing basis.

Subjects in dose escalation cohorts (numbered Cohorts 1, 2, 3, etc.) will return to the study center to complete safety assessments at Days 3, 4, 8, and 36 (EOS).

#### *Dose Expansion Cohort*

The highest well-tolerated dose (as determined by the DEC) will be evaluated in a dose expansion cohort in which subjects will receive treatment with EXN407 or vehicle for up to 3 months.

Subjects in the dose expansion cohort will return for safety and efficacy evaluations at Day 8, Day 15, Day 29, Day 57, Day 85 (treatment completion visit) and Day 113 (EOS Visit) post first dose, and will have a telephone contact at Day 22.

#### *DEC, Study MM, Sponsor MM and Investigator Communication Plan*

At each specific point at which key decisions are required, such as assessment of sentinel subjects, initiation of dosing in the remainder of the cohort, or any decision to dose escalate / de-escalate to an additional cohort, a decision will be made and documented by the DEC and the study MM ([REDACTED]) and also Sponsor MM. Details of the DEC's composition, roles and responsibilities will be described in a DEC charter. The Sponsor will chair the DEC,

which will be comprised of a Sponsor-led group. An analysis of safety and tolerability will be undertaken, discussed and a decision will be taken and documented for dose escalation, or dose de-escalation or to expand an existing cohort.

#### *Screening*

During the Screening period, subjects will be assessed according to the eligibility criteria. Measures of retinal structure and visual function including SD-OCT and BCVA will be measured twice, for Screening and pre-dose on Day 1 (baseline), prior to each subject's first dose of the randomized study drug or vehicle. Other measures of retinal anatomy such as CFP will be measured at least once prior to the subject's first dose of study drug. Fluorescein fundus angiography will be assessed at the Screening Visit. Any pre-dose assessment may be repeated if the results are considered unreliable or of unacceptable quality by the Investigator, or if the assessment could not be completed. In the case of repeat assessments, the measure reflecting the highest level of visual function will be considered the baseline value unless regarded as an implausible reading in the opinion of the Investigator. Structural tests will be averaged and used as the baseline (pre-treatment value).

Subjects who meet all eligibility criteria will be enrolled into the study and will receive their first dose of the study drug on Day 1. EXN407 or vehicle will be instilled into the subject's study eye under supervision of the Investigator (or delegate). Subjects will be monitored for signs of irritation and inflammation for an initial period of 2 hours post-dose, for their first dose on Day 1 only. Subjects in dose escalation cohorts (numbered cohorts 1, 2, 3, etc.) will additionally return to the clinic at Day 3 and Day 4.

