### **9.1. Subject Inclusion Criteria**

Subjects eligible for enrolment in the study must meet all of the following criteria at Screening and enrolment.

1. Subject is at least 18 years of age inclusive, at the time of signing the informed consent
2. BCVA better than or equal to a 69 ETDRS score (an approximate Snellen equivalent of 20/40 or 6/12) in the study eye using the ETDRS visual acuity scale at Screening or BCVA less than a 69 ETDRS score (an approximate Snellen equivalent of 20/50 or 6/15) but who, in the Investigator's opinion, is unsuitable for treatment with anti-VEGF by intravitreal injection or refuses it. Subjects should have no more than a 7-letter difference in BCVA at Screening and baseline visit.
3. A female subject is eligible to participate if she agrees to use highly effective contraceptive measures (if heterosexually active and a WOCBP) from Screening until study completion, including the follow-up period. Acceptable methods of contraception include the use of condoms AND the use of an effective contraceptive that includes:
  - a. Oral contraceptives (The Pill),
  - b. Long-acting implantable hormones,
  - c. Injectable hormones,
  - d. A vaginal ring or an IUD.Rhythm methods are not considered as highly effective methods of birth control.
4. A female subject must also not be breast feeding and must have a negative pregnancy test prior to start of dosing if of childbearing potential, or must have evidence of non-childbearing potential by fulfilling one of the following criteria at Screening:
  - e. Is postmenopausal defined as aged more than 50 years and amenorrheic for at least 12 months following cessation of all exogenous hormonal treatments.
  - f. Can provide documentation of irreversible surgical sterilization by hysterectomy, bilateral oophorectomy or bilateral salpingectomy but not tubal ligation.
  - g. Is amenorrheic for 12 months and serum follicle-stimulating hormone levels in the postmenopausal range for the institution.
5. Sexually active male subjects where the sexual partner is a WOCBP must be willing to use barrier contraception i.e., condoms, and another acceptable form of contraception (see Inclusion Criteria 3 for acceptable forms) during the study and for 3 months after the last dose of study medication.

6. Diabetes mellitus (Type 1 or Type 2). Any of the following will be considered to be sufficient evidence that diabetes is present:
  - a. Current regular use of insulin for the treatment of diabetes

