## 12.3. Dose Escalation (A) Cohorts 1, 2, 3, etc.

### 12.3.1. Visit 2A - Day of First Dosing (Day 1)

#### 12.3.1.1. Before Dosing

Prior to dosing on Day 1, subjects will be randomized to one of the following treatments:

- EXN407
- Placebo (vehicle)

The following assessments should be performed prior to the administration of study drug unless otherwise noted:

- A verbal check by the Investigator that the subject experienced no issues with self-administration of Systane® Ultra UD eye drops during the run-in period
- Concomitant Medications
- Documentation of AEs since the Screening Visit (from time of consent)
- Weight measurement
- Vital Sign Measurements - systolic and diastolic BP, heart rate, respiratory rate, body temperature
- Physical Exam - Complete physical examination including: general appearance, head, ears, eyes, nose, throat, thyroid, chest (heart, lungs), abdomen, skin, neurological, extremities, back, neck, musculoskeletal, and lymph nodes
- Single 12 lead ECG
- Urine sample collected for urinalysis
- Urine Pregnancy test (WOCBP only)
- Blood draw for hematology, serum chemistry and coagulation
- Ophthalmic Exam/ Ophthalmoscopy
- SD-OCT
- BCVA
- Tonometry to measure IOP
- Corneal pachymetry
- Investigator review of all eligibility criteria

If not performed already during Screening, the following measures of retinal anatomy will be measured (required to be completed at least once prior to the subject's first dose of study drug):

- CFP

Any pre-dose assessment may be repeated if the results are considered unreliable or of unacceptable quality by the Investigator, or if the assessment could not be completed. In the case

of repeat assessments, the measure reflecting the highest level of visual function will be considered the baseline value unless regarded as an implausible reading in the opinion of the Investigator. Structural tests will be averaged and used as the baseline (pre-treatment value).

Following final review of all eligibility criteria and randomization the study drug will be dispensed ready for administration.

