##### **14.1.7.3. BCVA**

BCVA will be performed using the ETDRS visual acuity measure at Screening and at other times according to the Schedule of Assessments ([Table 5](#)), to assess visual acuity. BCVA will be performed prior to procedures requiring pupil dilation.

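### Taking the highest repeated pre-dose visual acuity as baseline tilts the descriptive within-arm BCVA change toward loss (minor)

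*Combined protocol and SAP*

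**What the plan says.** The Screening part of the synopsis sets the trigger for a repeat: "Any pre-dose assessment may be repeated if the results are considered unreliable or of unacceptable quality by the Investigator". A test that could not be completed may also be repeated. The baseline then follows from "In the case of repeat assessments, the measure reflecting the highest level of visual function will be considered the baseline value", with one exception: "unless regarded as an implausible reading in the opinion of the Investigator". Section 12.3.1.1 repeats the rule for Day 1 of the escalation cohorts. Section 12.4.1.1, for the expansion cohort, does not restate it, but the synopsis text is not limited to one cohort type.

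Structural tests are handled differently: "Structural tests will be averaged and used as the baseline (pre-treatment value".

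Pre-dose BCVA is planned at Screening and on Day 1, and inclusion criterion 2 in Section 9.1 links the two: "Subjects should have no more than a 7-letter difference in BCVA at Screening and baseline visit". After dosing, Table 5 has one BCVA per visit at which it is scheduled.

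Baseline BCVA feeds the secondary change endpoint (Section 7.2.2) and the proportions gaining or losing 5, 10 and 15 letters (Section 18.3.6). Sections 8.5.1.1 and 8.5.3 also refer to it. Section 18 makes all analyses descriptive and defers detail to a SAP.

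**The concern.** The test for repeating a reading (doubtful) is not the test for discarding it (implausible). A first reading that was doubtful and falsely low loses to the repeat. One that was doubtful and falsely high, but still believable, wins and becomes baseline, although it was the reason for the repeat. If both readings were sound, the higher of the two still overstates true acuity on average.

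Nothing offsets this after dosing, because a single reading is then compared with the better of two. With no true change, a repeated subject tends to show an apparent loss and too little gain. What is at stake is the accuracy of within-arm descriptive summaries of a secondary endpoint.

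**Working it through.** The plan gives no figure to reproduce.

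**Inputs from the documents.** Baseline is the maximum of repeated readings. There is one scheduled reading per post-dose visit. The Screening-to-baseline difference is at most 7 letters. The expansion cohort has up to 40 subjects at 2:1, so about 40 x 2/3 = 27 on EXN407.

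**Assumptions.** Single-reading SD of 2.5, 3.5 or 5 letters; a faulty first reading off by 5 or 8 letters; 10-20% of subjects repeated; true score uniform over 69-85; independent normal errors; every reading rounded to a whole letter; no true change.

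**Step 1, two valid readings, no 7-letter limit.** The expected maximum of two independent normal readings exceeds the true value by SD/sqrt(pi) = 0.564 x SD. That is 1.41, 1.97 and 2.82 letters at SD 2.5, 3.5 and 5. Simulation agrees (mean change -1.4, -2.0 and -2.8).

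**Step 2, apply the limit.** Draw a Screening reading with no systematic error and keep the subject only if it lies within 7 letters of the baseline. The limit removes some of the highest baselines:

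- *Two valid readings:* mean change -1.3, -1.6 and -2.1 at SD 2.5, 3.5 and 5. At SD 3.5, loss of 5 or more letters is 26% and gain 8%, against 17% each with a single reading.
- *First reading 5 letters high, SD 3.5:* 33% of such subjects fail the limit. In the rest, mean change is -4.3, 5-letter loss 48% and 10-letter loss 12%.
- *First reading 8 letters high, SD 3.5:* 55% fail. In the rest, mean change is -6.1, 5-letter loss 64% and 10-letter loss 22%.
- *First reading 8 letters low, SD 3.5:* mean change about -0.05.
- *First test not completed:* there is only one reading to use, so the shift is zero.

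**Step 3, effect on an arm mean (SD 3.5).** If 10-20% of subjects had two valid readings, the shift is -1.64 x 0.10 = -0.16 to -1.64 x 0.20 = -0.33 letters. One subject in 27 with a falsely high first reading moves the mean by -4.26/27 = -0.16 or -6.05/27 = -0.22.

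**Step 4, scale.** Ignoring the limit, the standard error of an arm mean with n = 27 is sqrt(2 x 3.5^2)/sqrt(27) = 0.95 letters from measurement error alone. With an assumed true-change SD of 5 it is sqrt(2 x 3.5^2 + 5^2)/sqrt(27) = 1.35. The 10-20% shift is thus 0.16/1.35 = 0.12 to 0.33/0.95 = 0.35 of a standard error.

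**Step 5, between arms.** Repeats happen before dosing and under masking, so the rule acts alike in both arms. A simulation without the limit (27 v 13 subjects, SD 4, 10-50% repeated) gave a between-arm bias within 0.01 letters.

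**Step 6, alternative rule.** If the last valid Day 1 reading is baseline, mean change is 0.0 and 5-letter loss equals gain. The replaced reading is not used, so it does not matter whether it was high, low or incomplete.

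**The case against.** Much can be said for leaving this alone. Two valid readings should be uncommon, because a repeat requires a doubtful or incomplete first test. A falsely high baseline needs an Investigator who doubts a reading yet does not call it implausible. Falsely low and incomplete first tests do almost no harm. The rule may be deliberate, since Section 8.5.1.1 also uses a best-acuity reference, and the deferred SAP could settle the derivation. All of this limits the size and supports a low priority. It does not remove the bias: no section supplied withdraws the rule, and the stopping criteria name their own best in-study reference, so they do not need a maximum as baseline.

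A reader might infer more than the documents support:

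- *That the comparison with vehicle or the primary result is biased.* It is not: the between-arm difference is unbiased in expectation, and the primary endpoint is ocular adverse events.
- *That every subject is affected, because Screening and Day 1 form a repeated pair.* The synopsis plans these as two separate measurements, "including SD-OCT and BCVA will be measured twice, for Screening and pre-dose on Day 1 (baseline", Table 5 labels Day 1 as baseline, and the 7-letter criterion contrasts the two visits. The natural reading is that only quality repeats count, although no sentence expressly excludes the Screening value.
- *That planning of future trials would be misled.* Section 8.2 hopes to aid powering, but this depends mainly on the between-arm difference and the variability. The first is unbiased and no effect on the second has been shown.
- *That the shift is the full -2.0, -5.4 or -8.1 letters obtained at SD 3.5 without the 7-letter limit.* The criterion is worded as should, so these are upper bounds for those assumed errors.

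**Conclusion.** The point holds and is minor. Followed as written, the rule biases the descriptive within-arm BCVA change and the letter-gain and letter-loss proportions toward loss in subjects whose pre-dose BCVA was repeated and not merely completed. The direction follows from the rule. The size rests on assumed values for SD, error size and repeat frequency: at SD 3.5, from about 1.6 letters per repeated subject with two valid readings to 4-6 letters with a plausible but falsely high first reading, and a few tenths of a letter or less on an arm mean of about 27. A lean toward loss is the cautious direction for a safety summary. No effect on the vehicle contrast, the primary endpoint or the powering of later trials is claimed.

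**What to change.** In the synopsis, Section 12.3.1.1 and the SAP, for both eyes and both cohort types, define baseline BCVA for change summaries as the last valid Day 1 pre-dose reading. Allow a reading to be replaced only for a quality reason recorded at the time, other than the score itself, and do not use the replaced reading. State that the Screening reading serves eligibility only. Averaging, as for structural tests, is equally unbiased only when both readings are valid; otherwise it keeps part of the faulty one.

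The cost is small but not nil. It takes a few sentences and no new data or visits. Some Investigator judgment on validity remains. Sections 8.5.1.1 and 8.5.3 also refer to baseline BCVA and must be reconciled with the definition chosen; no clinical rule is proposed here.
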